This study will evaluate the changes in respiratory mechanics following TBI and determine the effect of inhaled nitric oxide on gas exchange.

4. Purpose of Study:

[figure not shown]
To determine the changes in respiratory mechanics in patients with traumatic brain injury (within 36 hours of admission and day 3 following admission).

To evaluate the effect of inhaled nitric oxide on gas exchange in patients with traumatic brain injury within 36 hours of admission.

Hypothesis: Inhaled nitric oxide improves oxygenation and reduces deadspace to tidal volume ratio following TBI.

5. Background:

Intubation and mechanical ventilation are common treatments in the care of patients with traumatic brain injury (TBI). Intubation allows for airway control and facilitates removal of respiratory secretions. Mechanical ventilation allows control of arterial carbon dioxide to aid in control of intracranial pressure. Recent evidence suggests that lung protective ventilation (tidal volumes of 6 ml/kg of predicted body weight and moderate positive end expiratory pressure) improves outcomes following brain injury and reduces brain-lung cross talk. Figure 1.

Respiratory failure following traumatic brain injury is a common complication resulting in hypoxemia and is associated with release of inflammatory mediators which may damage distal organs including the brain. The etiology of respiratory

failure following brain injury is multifactorial. Isolated head trauma is associated with neurogenic pulmonary edema and changes in ventilation perfusion matching. Concomitant trauma to the chest and pulmonary contusion may further worsen lung injury. It has been suggested that brain injury primes the lung to be a greater risk to a second hit (pneumonia, ventilator induced lung injury, lung contusion). Loss of consciousness can lead to aspiration of oral or gastric contents leading to pneumonia. Importantly, respiratory failure following TBI is implicated in 50% of deaths and prolonged ICU and hospital stay. (4,5)

The treatment of respiratory failure in TBI must balance the need to improve lung function with the negative consequences of increased intrathoracic pressure on mean arterial pressure, intracranial pressure and venous return. Traditional treatment of increasing PEEP and mean airway pressure then, represent competing interests. Methods for improving arterial oxygenation while avoiding negative hemodynamic effects are needed.

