5. Positive end expiratory pressure (PEEP) will be titrated from baseline PEEP as set at time of enrollment to 15 cm H_2O (in 5-cm H_2O increments) while measuring all the variables listed in #1-4 above. This method will determine the best PEEP and determine recruitability of the lung. FRC will be measured at three levels of PEEP from baseline to a maximum of 15 cm H_2O . This is an automated measurement requiring approximately 15 minutes to complete. If the patient develops hypotension (systolic pressure < 90 mm Hg or mean arterial pressure < 60 mm Hg) participation in the PEEP trial will be terminated.
6. Following these initial measurements, patients will be randomized to receive either a placebo (nitrogen and oxygen) or inhaled NO at 20 ppm for 2 hours \pm 30 minutes. After receiving the placebo or inhaled NO, the measurements in #1-4 will be reassessed (no change in PEEP will be made during this time unless required for clinical purposes).
7. If the patient remains on the ventilator at day 3 (72 hours after admission), 1-6 above will be repeated.

Subjects will receive placebo or drug for no more than 5 hours total.

If the patient responds to NO with a brisk increase in SpO₂ or PaO₂ – sudden withdrawal of NO can result in a fall in oxygenation (rebound pulmonary hypertension). This is uncommon in the absence of pulmonary hypertension. Prevention of rebound pulmonary hypertension is accomplished by increasing FIO₂ by 10-20% prior to discontinuation of NO, followed by a return to baseline FIO₂ over 30 mins.

If ICP goes up by >20% NO will be discontinued.

7. Research data collection/study procedures:

The patient baseline demographics including injury mechanism, severity and distribution, Glasgow coma scale score, age, gender, any witnessed aspiration, and lung mechanics measurements listed above will be collected to data sheets and then entered into a RedCap database. We will also record ventilator settings, lung compliance, airways resistance, dead space to tidal volume ratio, functional residual capacity, blood gases and duration of total mechanical ventilation, days in the ICU, hospital days and survival will be collected from the medical record and also entered into the RedCap database. See sequence of events for study measures.

8. Specimen collection:

The following blood samples will be taken:

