At baseline up to 3.5 ml will be taken. 1.5 ml for arterial blood gas testing (tests include: arterial pH, PaCO₂, PaO₂, SaO₂ and HCO₃) and 2 ml for measurement of inflammatory mediators specific to the lung.

After 90 to 120 minutes of nitric oxide/placebo delivery, less than 1.5 ml will be taken for arterial blood gas testing.

At the end of the study, up to 3.5 ml will be taken. 1.5 ml for arterial blood gas and 2 ml for measurement of inflammatory mediators specific to the lung.

The blood will be taken from indwelling lines when possible. If we are unable to obtain any of the blood samples, the subject will remain in the study and all other data will continue to be collected

9. Potential Benefits:

The detailed measurement of respiratory mechanics will be provided to the clinical team. This information which is not routinely measured can be used to optimize ventilator support beyond traditional monitoring. The determination of FRC and recruitability of the lung may assist the clinical team in identifying the best PEEP for each individual patient.

If the patient has a significant increase in PaO_2 associated with INO/placebo delivery, the clinical team can use that information to implement INO therapy as part of clinical care. It is unlikely that placebo will increase oxygenation appreciably. We will not unblind the study, the clinical team will have to make this decision based on a supposition of INO delivery.

Understanding the changes in respiratory function following TBI and the response to INO may improve treatment regimens for future patients.

10. Potential Risks, Discomforts, and inconveniences:

Level of risk: Greater than minimal risk.

The measurements to be made utilize non-invasive measures of lung volumes, flows, and pressures to determine mechanics.

Arterial puncture/venipuncture may cause pain/discomfort, bruising, fainting, and infection from phlebotomy sites.

Hypotension in severe pulmonary hypertension and left ventricular failure (very uncommon).

Methemoglobinemia has only been reported at 80ppm.

The stepwise increase in PEEP to determine changes in FRC will be limited to a maximum of 15 cm H_2O . PEEP can decrease venous return and cause transient hypotension. The risk of hemodynamic compromise at these low pressures is small. All subjects will have blood pressure and heart rate continuously monitored (as is standard of care) throughout the measurements.

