Research personnel will remain at the bedside throughout the measurements of respiratory mechanics which will require approximately 30 minutes to complete.

11. Data Safety monitoring plan and/or DSMB:

[name] will act as medical monitor for the study. He will review subjects' research data and adverse events to ensure patient safety. The medical

monitor will have the power to temporarily or permanently halt enrollment if it is deemed that patient safety is compromised.

12. Data Analysis:

Descriptive statistics will be employed to summarize relevant patient demographic factors as well as on baseline measurement of clinical variables. As a check on the success of randomization, these variables will be compared between groups using t-tests or chi-square tests, as appropriate.

The primary endpoint for this study is a change in $\text{PaO}_2:\text{FiO}_2$ ratio of 20 percent or greater between baseline and Day 3. The proportions of patients achieving success according to this criterion will be compared between groups using a two-sided z-test with pooled variance.

Group sample sizes of 19 in group one and 19 in group two achieve 82% power to detect a difference between the group proportions of 0.40. The proportion in group one (the treatment group) is assumed to be 0.10 under the null hypothesis and 0.50 under the alternative hypothesis. The proportion in group two (the control group) is 0.10. The test statistic used is the two-sided Z test with pooled variance. The significance level of the test was targeted at 0.05. The significance level actually achieved by this design is 0.0361.

Respiratory mechanics will be presented as descriptive (Mean, SD, range). Up to 43 subjects may be enrolled, in order to obtain the required 38 evaluable subjects. Patients will be removed from the study and its analysis if extubated by the clinical treatment team during the 72 hour NO protocol.

13. Data storage and confidentiality (include sample storage if applicable)

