We will ensure that paper forms are stored securely under lock and key when not in the direct custody of an investigator. Forms may have direct identifiers for the purposes of linking data from different medical records. Electronic data will not be entered with direct identifiers. A subject number will be used to link back to the identifier. The key linking identifier to subject number will not be stored with the electronic data. Electronic data will be stored in a password protected Redcap database. Analytical datasets will be stored on secure servers that also limit access to the investigator team. Should results of the study be published or reported, individual names or other identifying information will not be used. One year after the study and publication are complete the data will be destroyed.

14. Study Population

All subjects ≥ 18 and ≤ 75 years of age, admitted to the University of Cincinnati Medical Center with traumatic head injury requiring mechanical ventilation within 24 hours of admission will be screened for enrollment. Inclusion criteria will include:

1. TBI with head CT findings of injury by penetrating or blunt mechanism
2. Requiring mechanical ventilation within 24 hours of admission
3. Negative pregnancy test

Exclusion criteria will include:

1. Brain death
2. Expected survival < 48 hours
3. Pneumothorax causing chest tube to be placed
4. Elevated inspired oxygen concentration ($\text{FiO}_2 > 0.65$) on assessment
5. Hemodynamic instability (systolic BP < 100 mmHg, cardiac arrhythmias)
6. Uncontrolled ICP (>20 mmHg) necessitating bolus hypertonic saline therapy
7. Unilateral or bilateral pupil dilation and no reactive pupil
8. Spinal cord injury with hypotension
9. Severe ARDS ($\text{PaO}_2/\text{FIO}_2 < 100$)
10. Flail sternum or unilateral flail chest wall segment (2 places on ≥ 3 ribs)
11. Pulmonary contusion or lobar infiltrate visible on admission chest xray
12. Chronic lung disease with $\text{PCO}_2 > 60$ mmHg and $\text{HCO}_3^- > 32$ mmol/L
13. ICP >20 mmHg longer than 30 minutes despite hypertonic saline or mannitol therapy
14. Known heart failure (heart failure defined as EF < 20%)
15. CVP > 20 mm Hg with associated systolic blood pressure < 100 mmHg

15. Consenting process and plan

Study personnel will screen patients for inclusion and exclusion.

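### Section 12 drops randomised patients who are extubated during the 72-hour protocol, so the primary Day 3 comparison does not cover the groups as randomised and may be biased in either direction

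*Combined protocol and SAP*

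**What the plan says.** Randomisation takes place in the first session, after baseline measurements made within 36 hours of admission (section 6, Study design, item 6). The primary endpoint in section 12 (Data Analysis) is binary: a PaO2:FiO2 change of at least 20 percent from baseline to Day 3. It is compared between arms with a two-sided pooled z-test.

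Section 12 then sets the analysis population. It allows for losses, "Up to 43 subjects may be enrolled, in order to obtain the required 38 evaluable subjects", and adds: "Patients will be removed from the study and its analysis if extubated by the clinical treatment team during the 72 hour NO protocol".

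Other parts of the protocol bear on this rule:

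- Section 6, item 7, makes only the repeat session conditional: "If the patient remains on the ventilator at day 3 (72 hours after admission), 1-6 above will be repeated".
- Section 4 (Purpose of Study) gives an aim that session 1 alone can serve: "To evaluate the effect of inhaled nitric oxide on gas exchange in patients with traumatic brain injury within 36 hours of admission".
- Section 7 lists outcomes that do not depend on ventilation at 72 hours: "duration of total mechanical ventilation, days in the ICU, hospital days and survival will be collected from the medical record".
- Section 8 treats a missing blood sample the other way: "the subject will remain in the study and all other data will continue to be collected".
- Section 14 excludes patients with "Expected survival < 48 hours", while Day 3 is 72 hours after admission.

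There is no statement that all randomised patients will be analysed, no rule for a missing Day 3 value, no expected extubation rate, no reporting of removals by arm and no sensitivity analysis.

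**The concern.** Removal depends on something that happens after randomisation, is decided by clinicians, and is plausibly linked to lung function. Patients who improve may come off the ventilator sooner, or extubation may follow neurological recovery with little relation to oxygenation; the documents do not say. In either case the primary test compares those who remain ventilated, and randomisation no longer guarantees that they are alike.

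The condition for no bias under the null is narrower than equal extubation rates. Removal must not depend on arm among patients with the same outcome. Even when that holds, the estimated difference can shift if there is a true effect.

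The rule also reaches further than it needs to. Section 6, item 7, already lets an extubated patient simply miss the repeat session. Removal from the study as well as the analysis, read literally, takes out session-1 gas exchange and mechanics and the medical-record outcomes. For duration of ventilation and ICU stay, it would leave a sample tilted toward patients ventilated longer.

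**Working it through.** **Inputs from section 12.** 19 per arm; success proportions 0.50 (INO) and 0.10 (control); two-sided pooled z-test at 0.05; up to 43 enrolled for 38 evaluable, which leaves 5 spare places (5/43 = 11.6%). Every extubation rate below is an assumption.

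**1. The plan's own figures.** With x successes of n1 and y of n2, and p̄ = (x+y)/(n1+n2),

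z = (x/n1 − y/n2) / √[p̄(1−p̄)(1/n1+1/n2)].

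Summing binomial probabilities over all (x, y) with |z| ≥ 1.96 at 19/19 gives power 0.815 and significance level 0.0361. These match the stated 82% and 0.0361. Power is 0.785 at 18/18 and 0.750 at 17/17.

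**2. How far five removed patients could move a result.** Assume that all 5 spare places are extubations and that 22 INO and 21 control patients were randomised, so 3 INO and 2 control patients are missing. Their successes can be 0–3 and 0–2, which gives 4 × 3 = 12 combinations. The z-test is recomputed at 22/21 for each.

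| Observed (19/19) | Observed p | Range of p over 12 restorations | Above 0.05 |
|---|---|---|---|
| 10 vs 2 | 0.005 | 0.0007 (13/22 vs 2/21) to 0.065 (10/22 vs 4/21) | 1 of 12 |
| 9 vs 2 | 0.012 | 0.0016 to 0.119 | 3 of 12 |
| 8 vs 2 | 0.027 | 0.0039 to 0.206 | 5 of 12 |

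These are counts of possible outcomes, not probabilities. With 21/22 randomised, the first row runs from 0.0008 to 0.087, again with one case above 0.05.

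**3. Selection at the same rates in both arms.** If a share qs of successes and qf of non-successes is removed, the observed proportion is p(1−qs) / [p(1−qs) + (1−p)(1−qf)].

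- qs = 0.40, qf = 0.10. INO: 0.30/(0.30+0.45) = 0.400. Control: 0.06/(0.06+0.81) = 0.069. The difference falls from 0.40 to 0.331, and power at 19/19 from 0.815 to 0.718.
- qs = 0.10, qf = 0.30. INO: 0.45/(0.45+0.35) = 0.5625. Control: 0.09/(0.09+0.63) = 0.125. The difference rises to 0.4375. Power would be 0.862 if 19/19 were still available. But the expected numbers left are 22 × 0.80 = 17.6 and 21 × 0.72 = 15.1, and at 18/15 power is about 78%.

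So the apparent effect can shrink or grow. With no true effect, equal qs and qf in both arms give equal observed proportions.

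**4. Removal that depends on arm, with no true effect.** True success is 0.10 in both arms, and 30% of INO non-successes and no controls are removed. Observed INO proportion: 0.10/(0.10 + 0.90 × 0.70) = 0.137, against 0.10. The rejection rate at 19/19 is 5.5% instead of 3.6%; at the expected 16/21 it is about 6.7%. This takes out about 22 × 0.90 × 0.30 = 5.9 INO patients, more than all the spare places, so it is a severe case.

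**The case against.** The strongest reply is that no bias has been shown. Study gas runs for about two hours per session, delivery is blinded, and nothing in the documents says that extubation differs by arm. Section 9 (Potential Benefits) says that, after a PaO2 rise, "the clinical team can use that information to implement INO therapy as part of clinical care". A reader might infer from this that extubation depends on arm. The passage is about starting INO, not about extubation. It shows only that blinded clinicians may act on the response to the gas, so dependence is possible but not established. A result near the design assumption is also fairly robust: 11 of the 12 restorations of 10/19 vs 2/19 stay below 0.05. And the bounds assign outcomes to patients whose Day 3 value does not exist under the protocol. All of this stands, and it limits the claim to possible bias of unknown size.

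A reader might also infer that the removed patients' data are destroyed. The documents do not say so. Section 13 sets destruction at one year after the study and publication are complete, and section 6, item 7, can be read as letting extubated patients skip one session. What the wording supports is exclusion from analysis.

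Nor is the 82% power wrong. It is stated for 19 and 19, and section 12 calls 38 evaluable patients the required number.

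What the reply does not remove is the rule itself. Section 12 explicitly excludes randomised patients on a post-randomisation event, and no other section brings them back.

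**Conclusion.** The concern holds as a defect in the definition of the primary analysis population, and it should be corrected before unblinding. The Day 3 comparison does not cover the groups as randomised. Bias may run either way or be absent, and the documents do not allow its size or direction to be determined. It would go too far to say that the result will favour INO, or that the type I error is known to be inflated.

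The practical size is that of a small trial. If five removals are assumed, they could carry a moderately significant result across 0.05 (3 of 12 restorations for 9/19 vs 2/19, 5 of 12 for 8/19 vs 2/19), but a strong one in only one corner. These counts rest on near-equal allocation and on all five losses being extubations, which section 12 does not state. Sections 6 and 12 need to be reconciled on what happens to an extubated patient. The timing matters because, once arms are known, any replacement rule could be chosen with the result in view.

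**What to change.** Replace the removal sentence in section 12 with text that does the following:

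- Keeps every randomised patient in the assigned arm. Because section 6, item 7, repeats the randomising step, it should also say which assignment defines the arm.
- Analyses session-1 gas exchange and mechanics and the medical-record outcomes for all randomised patients. Extubation then makes only the Day 3 measurement unavailable.
- Fixes, before unblinding and identically in both arms, how extubation before Day 3 enters the primary endpoint, and likewise death before Day 3, and states the estimand this implies. The choice is the sponsor's.
- Reports extubations and deaths by arm.
- Adds best-case and worst-case bounds, and keeps the still-ventilated comparison as a supplementary analysis labelled as not covering the groups as randomised.
- Restates power under the chosen strategy.

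No new measurements are needed, but this redefines the endpoint and is more than a wording change. Counting extubation as non-success may label recovery as failure; counting it as success dilutes the contrast. Suppose all 43 are kept and a fraction e is extubated regardless of outcome. The proportions become p(1−e) under non-success coding and p(1−e)+e under success coding. Exact power over 22/21 and 21/22 is then:

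| Assumed e | Non-success | Success |
|---|---|---|
| 10% | 0.45 vs 0.09: about 79–80% | 0.55 vs 0.19: about 72–74% |
| 20% | 0.40 vs 0.08: about 72–74% | 0.60 vs 0.28: about 61–63% |

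If the chosen strategy puts power below what the sponsor accepts, the sample size must be revisited.

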All subjects \geq 18 years of age, admitted to the University of Cincinnati Medical Center with traumatic head injury requiring mechanical ventilation within 24 hours of admission will be screened for enrollment.

Following informed consent, patients will have assessments of respiratory function accomplished using the existing monitors within the mechanical ventilator. The NM3 respiratory monitor and airway sensor will be placed for continuous recording of data. Within 36 hours of admission, the following measurements will be made by the study staff:

1. Static and dynamic lung compliance using tidal volume and airway pressures ($CL_{static} = P_{plat} - P_{PEEP}/VT$) $CL_{dynamic} = P_{plat} - P_{PEEP}/VT$). These measurements are made non-invasively using the integral monitoring of the mechanical ventilator.
2. Airway resistance using airway pressures and flow ($Raw = P_{plat} - P_{PEEP}/Mid Expiratory flow$). These measurements are made non-invasively using the integral monitoring of the mechanical ventilator.
3. Dead space to tidal volume ratio (V_d/V_t) will be calculated using the Enghoff modification of the Bohr equation: $V_d/V_t = PaCO_2 - PeCO_2/PaCO_2$, where V_d is the dead space volume and V_t is the tidal volume; $PaCO_2$ is the partial pressure of carbon dioxide in the arterial blood, and $PeCO_2$ is the mixed expired partial pressure of carbon dioxide in the expired (exhaled) air. In the absence of arterial blood gases we will calculate $PaCO_2$ from determination of alveolar concentrations ($PaCO_2$) in expired gas.
4. Functional residual capacity (FRC) will be measured by the automated system within the GE Carestation ventilator, which uses a step change in FIO_2 to measure FRC through nitrogen washout while monitoring oxygen consumption and carbon dioxide production. These measurements are made non-invasively using the integral monitoring of the mechanical ventilator.

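### Removing patients extubated before 72 hours from the study, with no exception for harm data, can leave exposed patients out of the final safety and survival figures

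*Combined protocol and SAP*

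**What the plan says.** Section 12 (Data Analysis) ends with the rule: "Patients will be removed from the study and its analysis if extubated by the clinical treatment team during the 72 hour NO protocol". The sentence before it sets the numbers: "Up to 43 subjects may be enrolled, in order to obtain the required 38 evaluable subjects".

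Section 6 (Study design) fixes the timing. "Within 36 hours of admission, the following measurements will be made by the study staff"; after these, under item 6, "patients will be randomized to receive either a placebo (nitrogen and oxygen) or inhaled NO at 20 ppm for 2 hours", with a tolerance of 30 minutes either way. Section 4 gives the same time frame for the aim: "To evaluate the effect of inhaled nitric oxide on gas exchange in patients with traumatic brain injury within 36 hours of admission". Item 7 of section 6 then says: "If the patient remains on the ventilator at day 3 (72 hours after admission), 1-6 above will be repeated". A stop rule after item 7 ends NO if ICP rises by more than 20%.

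Three other places bear on what happens to a removed patient:

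- Section 7 (Research data collection) says that "days in the ICU, hospital days and survival will be collected from the medical record", without naming an analysis set.
- Section 11 (Data Safety monitoring plan) has a medical monitor review subjects' "research data and adverse events to ensure patient safety", and does not mention removed patients.
- Section 8 (Specimen collection) keeps a patient in the study when a blood sample cannot be obtained. It does not deal with extubation.

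No safety population is defined. Section 12 plans no tabulation of adverse events, gas stops or deaths.

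**The concern.** Extubation is decided by the clinical team after randomisation and, for many patients, after exposure to study gas. A missing Day 3 measurement is a reason why such a patient cannot contribute to a Day 3 endpoint. It is no reason to stop following the patient for harm or to leave out harm already recorded. Item 7 already limits the Day 3 repeat to patients still ventilated, so removal from the study is not needed for that purpose.

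The protocol rates its own risk as more than minimal and carries an ICP stop rule. With about 40 exposed patients, harm will be judged from a handful of events. A final report that follows the rule as written would drop some exposed patients from both numerator and denominator, together with any events or deaths they had.

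This point is about harm data only. The effect of the same rule on the primary comparison is a separate matter.

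**Working it through.** **Can an exposed patient be removed?** Inputs: initial measurements within 36 hours of admission (section 6); gas for 2 hours, at most 2.5 with the tolerance (item 6); Day 3 at 72 hours after admission (item 7). Assume gas starts by hour 36, in line with the aim in section 4.

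- Latest end of the first session: 36 + 2.5 = 38.5 hours.
- Time left before hour 72: 72 − 38.5 = 33.5 hours, and more if gas starts earlier.

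The answer is yes. The rule does not touch a patient who dies while intubated, and a patient extubated before gas was never exposed.

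**Does anything keep that patient's harm data?** Section 7 collects survival, section 11 provides review, and section 8 retains patients with missed blood samples. None of them mentions a patient removed for extubation.

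**The plan's own figures.** Exact enumeration of the two-sided pooled Z test with 19 per group reproduces the stated design. Power for 0.50 against 0.10 is 0.815 (stated 82%) and the achieved alpha is 0.0361 (as stated). The allowance for non-evaluable patients is 43 − 38 = 5, or 5/43 = 11.6% of those enrolled. The plan does not tie this allowance to extubation.

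**How much could be lost?** The documents give no extubation or event rates, so this is an illustration. Suppose m of the 5 non-evaluable patients received gas and were then extubated, and the others never started gas. Then N = 38 + m patients were exposed. With k patients having an event, unrelated to extubation:

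- P(at least one omitted) = 1 − C(N − m, k) / C(N, k)
- Expected number omitted = k × m / N

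| m | N | P, k = 3 | P, k = 5 | Expected omitted, k = 3 |
|---|---|---|---|---|
| 1 | 39 | 0.077 | 0.128 | 3 × 1/39 = 0.08 |
| 3 | 41 | 0.209 | 0.330 | 3 × 3/41 = 0.22 |
| 5 | 43 | 0.316 | 0.479 | 3 × 5/43 = 0.35 |

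For example, with m = 3 and k = 3: 1 − C(38, 3)/C(41, 3) = 1 − 8436/10660 = 0.209.

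**If no event is seen in the NO arm.** The Clopper-Pearson upper limit (two-sided 95%) is 1 − 0.025^(1/n):

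- n = 19 (evaluable patients only): 17.6%
- n = 20 (one removed NO patient kept): 16.8%
- n = 22 (three removed NO patients kept): 15.4%

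**The case against.** The strongest reply is that the rule damages an analysis the plan does not contain. Section 12 lists baseline summaries, the oxygenation responder comparison and descriptive respiratory mechanics. It promises no harm table, and nothing says one would be built on the evaluable set. The sentence also follows directly on the one about 38 evaluable patients, so it may have been meant only to say who is not evaluable for a Day 3 endpoint. The existing harm channels are not limited to evaluable patients: the monitor's review and the collection of survival carry no such restriction. Gas stops for an ICP rise happen while gas is running and would be on record before any later extubation. Finally, the numbers are small and rest on chosen inputs. The fall to 15.4% needs all three removed patients to be in the NO arm; with two of three (n = 21) the limit is 16.1%. Pooling the arms, the one-sided 95% bound for an unseen harm is 7.6% with 38 patients and 6.7% with 43.

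Much of this stands. It narrows the point to final tabulation and to events and deaths after extubation, and it keeps the size modest. Section 7 also refers to a sequence of events that is not in the text available, so the absence of a retention rule is established only for what can be read.

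The narrower reading does not fit the words, which remove the patient from the study and separately from the analysis. Section 8 shows that the authors wrote an explicit retention rule when they wanted one. Review during the trial does not repair a final table, and nothing says that follow-up continues after removal.

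**Conclusion.** The concern holds. As written, the rule takes randomised and exposed patients out of the study on a post-randomisation event, and no section that can be read keeps their harm or survival data. The consequence is conditional: it arises if the final harm or survival figures follow the written rule.

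The size is modest. With 1 to 5 exposed patients removed, the chance of losing at least one event runs from 8% to 32% for 3 events and from 13% to 48% for 5 events. The expected loss is 0.08 to 0.35 of 3 events. These figures assume that events are unrelated to extubation, and the numbers of removed patients and events are assumed.

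The direction of any bias cannot be fixed from the documents. If patients extubated because they recovered are dropped, the apparent death rate rises. If patients who die after extubation are dropped, deaths are missed. The power and alpha calculations are not affected.

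**What to change.** Reword the last sentence of section 12, for example: *A patient extubated before 72 hours has no Day 3 measurements but stays in the study, with adverse events and survival still collected.* Name a safety set of everyone who started study gas, and summarise adverse events, early gas stops and deaths in it descriptively, by assigned arm.

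The cost is one reworded sentence and one named analysis set. Survival already comes from the medical record, so extubated patients need no extra procedure. Sample size, power and alpha stay as they are. The one drawback is that the report must show two denominators: up to 43 for safety and 38 for the evaluable analysis.
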